7.4.2 SAE Recording and Reporting Procedures

Serious AEs will be recorded on the SAE CRF and health authorities will be notified as outlined in Section 7.5.2. All centers are obligated to report SAEs within 24 hours of their occurrence and/or the sites knowledge of the event to the SACCC. The following attributes will be assigned:

- Description
- Date of onset and resolution (if known when reported)
- Severity
- Assessment of relatedness to test article
- Action taken

The site investigator will apply his/her clinical judgment to determine whether an adverse event is of sufficient severity to require that the subject be removed from treatment. If necessary, an investigator will suspend any trial procedures and institute the necessary medical therapy to protect a subject from any immediate danger.

Subsequent review by FDA, the DSMB, ethics review committee or IRB, or the sponsor(s) may suspend further trial treatment or procedures at a site. The study sponsor(s), FDA and DSMB retain the authority to suspend additional enrollment and treatments for the entire study as applicable.

A subject may voluntarily withdraw from treatment due to what he/she perceives as an intolerable AE, or for any other reason. If voluntary withdrawal is requested, the subject should

be asked to continue (at least limited) scheduled evaluations, and the study staff will complete a dosing termination form, and the subject will be given appropriate care under medical supervision until the symptoms of any AE resolve or their condition becomes stable.

7.4.2.1 REPORTING CRITERIA

Figure 1: Reporting Decisions for Adverse Events

- 1. Notify the site's investigator.
- 2. Complete and transmit an AE Form through the Internet data entry system. Information regarding a SAE report must be recorded in the subject's medical chart.
- 3. SAE follow-up reports should include hospital admittance notes, hospital discharge summary, clinical notes, resolution date, treatment and any other pertinent information regarding the event. Reporting should not be delayed in order to provide these documents.
- 4. In the event of a death, the SAE Form must be completed and transmitted along with other supporting data (e.g., death certificate, medical notes, etc.)

7.5 Serious Adverse Event Notification

7.5.1 Notifying the Sponsor

The Consortium of Food Allergy Research (CoFAR) investigators will provide the SACCC with data of all SAEs as defined per the protocol on an ongoing basis.

The CRO Medical Officer is responsible for notifying the sponsor and will do so simultaneously with the reporting to the clinical database. As noted above, this should be within 24 hours of site awareness of the event. The DAIT/NIAID/NIH Medical Monitor will review each SAE report and will determine whether the SAE must be reported to FDA on an expedited basis. The final decision for disposition regarding reporting to the FDA rests with the DAIT/NIAID/NIH Medical Monitor. The IND Sponsor is responsible for submitting the SAE reports to FDA. DAIT/NIAID/NIH will provide the DSMB with any safety report submitted to FDA. The SACCC will maintain copies of any SAE reports submitted to FDA by the sponsor.

The SACCC will provide these expedited reports to the individual site investigators. Events that are serious, related to therapy and unexpected will be reported to FDA in 15 days or for deaths and life threatening events in 7 days (per 21 CFR 312.32).

7.5.2 Notifying FDA and the Data and Safety Monitoring Board

After the SAE has been reported by the principal investigator and assessed by the IND sponsor, the IND sponsor must report the event to the appropriate health authorities using one of these two options:

- **Standard reporting (report in the IND annual report).** This option applies if the AE is classified as one of the following:
 - 1. Serious, expected, suspected adverse reactions described in Sections 7.2.2 and 7.2.3.
 - 2. Serious and not a suspected adverse reaction described in Section 7.2.2 and 7.2.3.
- **Expedited reporting is required.** This option applies if the AE is classified as one of the following:
 - Serious and unexpected suspected adverse reactions described in Section 7.2.2, and Section 7.2.3.
 - The sponsor must report any suspected adverse reaction that is both serious and unexpected. The sponsor must report an adverse event as a suspected adverse reaction only if there is evidence to suggest a causal relationship between the study drug and the adverse event, such as:
 - A single occurrence of an event that is uncommon and known to be strongly associated with drug exposure.
 - One or more occurrences of an event that is not commonly associated with drug exposure, but is otherwise uncommon in the population exposed to the drug.
 - Aggregate analysis of specific serious adverse events observed in a clinical trial (such as known consequences of the underlying disease or condition under investigation or other events that commonly occur in the study population independent of drug therapy) that indicates those events occur more frequently in the drug treatment group than in a concurrent or historical control group.
 - Any findings from clinical or epidemiological studies, analysis of data pooled across multiple studies, published or unpublished scientific papers, or from animal or in vitro testing that would result in a safety-related change in the protocol, informed consent, General Investigational Plan section of the IND or other aspects of the overall conduct of the trial.

Safety reports must be reported by the IND sponsor to the appropriate health authorities within 15 calendar days; fatal or immediately life-threatening, serious, unexpected, suspected adverse reactions must be reported within 7 calendar days.

All principal investigators must report SAEs to their respective IRBs as mandated by them.

7.5.3 Reporting SAEs to the DSMB

The DAIT/NIAID/NIH will provide the DSMB with data of all SAEs on an ongoing basis.

7.5.4 Notifying the Institutional Review Board and Ethics Committee

The investigator will ensure the timely dissemination of all AE information, including expedited reports and DSMB safety reviews, to the IRB and EC in accordance with applicable local regulations and guidelines.

8. Mechanistic Assays

Complementary studies will be performed to measure cellular and humoral immune responses at baseline and longitudinally. These assays have been selected based on hypothesized mechanisms of sustained unresponsiveness induction. The assays to be performed include:

- immune phenotyping of antigen-specific T cells, with a focus on cytokine production and homing molecule expression, in peripheral blood by FACS
- systemic and antigen-induced basophil activation assays
- measurement of whole antigen and epitope-specific IgE and IgG levels
- transcriptional analysis of whole blood and allergen re-stimulated PBMCs

The phenotype of antigen-specific T cells will be monitored at baseline and throughout immunotherapy using freshly isolated peripheral blood mononuclear cells re-stimulated with allergen *in vitro*. Phenotyping will be performed by flow cytometry, and will assess cytokine profile and chemokine receptor expression in antigen-responsive CD154+ CD4+ T cells. Additional phenotyping will be performed by transcriptional analysis of RNA isolated from the allergen-restimulated peripheral blood mononuclear cells.

To perform these assays, blood specimens will be obtained at screening (Visit 00), at 3 months (Visit 02), 6 months (Visit 03), at the 1 year 7444 mg egg white protein OFC (Visit 04), at the 2 year desensitization OFC (Visit 07), prior to the sustained unresponsiveness portion of the 2 year challenge and approximately 6 months after the sustained unresponsiveness challenge.

Subjects that pass the 2 year 7444 mg egg white protein OFC will stop their Egg OIT dosing and return in approximately 8-10 weeks for a 7444 mg egg white protein OFC off therapy (Visit 08) to test for sustained unresponsiveness and have a mechanistic blood test. Blood volumes must be no more than 50 cc in a day.

In summary, all 130 subjects entering the study will have specimens drawn as specified in this section.

At screening, 3 months, 6 months, and the 1 year OFC and 2 year OFC visits and at the 6 month follow up, up to 50 ml of venous blood (but no more than 5cc/kg in 24hrs or 9.5 cc/kg in 8 weeks) will be obtained. For optimal results, this volume includes 3 ml collected in a TempusTM tube for the purpose of RNA isolation, 3.5 ml for basophil studies, and the remainder subjected to mononuclear cell isolation at Mount Sinai. This PBMC sample will be utilized for T cell phenotyping studies by flow cytometry and transcriptional analysis. At the other time points, blood is drawn for basophil, IgE and IgG4 assessments and requires less blood volume (up to 10 ml).

Approximately 33 ml of whole blood plus the Tempus tube will be shipped overnight in thermally protected shipping containers to Mount Sinai for PBMC isolation and T cell immunophenotyping and profiling studies. This includes 20 ml for T cell phenotyping by flow cytometry, and 13 ml of blood for transcriptional analysis. 3.5 milliliters of blood will be retained at the site laboratories for basophil activation studies, i.e., antigen activation, staining and fixing as outlined in the MOP, and then shipped to the Mount Sinai Lab for cytoflow acquisition.

8.1 PBMC Assays

Immune responses to egg antigen will be assessed by stimulating PBMC in vitro and analyzing the phenotype of antigen-specific (CD154+) CD4+ T cells by flow cytometry. For this study, 4 x 10^{6} PBMCs will be cultured in egg antigen (1 mg/ml), media alone as negative control, or CD3/CD28 stimulator beads as positive control. Media will be AimV containing 2.5% autologous plasma. Duplicate cultures will be performed for media and antigen-stimulated cultures. Short-term stimulation (6h) will be performed followed by staining of cells as described in the sections below. Twenty million PBMCs are needed for this analysis.

The overall objective of ingestion of baked-egg products and egg OIT is to down-regulate allergen-specific Th2 responses in patients with egg allergy. Induction of sustained unresponsiveness suggests a shift in the type of CD4+ T cell responses specific for egg-associated antigens. To investigate this, we will apply a novel assay, which also has been reported by others in the evaluation of allergen-specific Th cell activation. ⁸⁹ This assay is based on the fact that antigen-specific CD4+ T cells can be detected by CD154 expression after short-term (6h) stimulation *in vitro*.

1. Analysis of circulating CD4+ T cells that help humoral responses: Studies have shown that T follicular helper (Tfh) cells are a Th subset specialized for provision of help to B cells. Tfh cells and their precursors play a critical role in the formation of germinal centers (GCs), ^{90,91,92} a structure where high-affinity B cells are selected through somatic hypermutation.⁹³ Tfh cells express the chemokine receptor CXCR5, which guides them to migrate into B cell follicles,⁹⁴ and secrete IL-21, a yc family cytokine that potently induces B cells to undergo proliferation, differentiation, and class-switching. Accordingly, Tfh cells promote proliferation and survival of B cells in GCs, and eventually induce their differentiation into either long-lived plasma cells or memory B cells capable of producing high-affinity antibodies. In human blood, a fraction of memory CD4+ T cells express CXCR5. Th2- and Th17-type Tfh cells, but not Th1-type Tfh cells produce IL-21, which promotes the differentiation and class-switching of naïve B cells. Th2-type Tfh cells are the most potent at inducing naïve B cells to produce IgE, while Th17-type Tfh cells are the most potent at promoting IgA production.⁹⁵ The analysis of blood CD4+ Tfh subsets may provide a more accurate reflection of the effects of egg OIT on changes in the composition of CD4+ T cell responses during immunotherapy and may better correlate with desensitization and sustained unresponsiveness induction. We will use a panel of monoclonal antibodies to assess the antigen-specific cytokine expression profiles in the blood Tfh compartment. The panel contains CXCR5, as well as four (4) cytokines, IL-4, IL-10, IL-13, and IFN- γ . CD154 up-regulation on CD4+ T cells cultured with egg protein, but not antigen control, will delineate activated egg-specific CD4+ T cells. Dead cells will be excluded using fixable Live/Dead dye. In addition to focusing on the Tfh cells, we will also determine the impact of intervention on cytokine expression in the total antigen-responsive (CD154^{pos}) population.

2. Analysis of homing antigen-specific T cells:

Our expectation is that oral immunotherapy or baked egg diet will reduce Th2 skewing of egg antigen-specific T cells, and that this will be associated with the development of sustained unresponsiveness to egg.

This analysis will be essential to understand the treatment-related changes in blood leukocytes. We anticipate that in subjects treated with either baked-egg or egg OIT, the induction of allergen sustained unresponsiveness will be accompanied by changes in the blood CD4+ T cell compartment including a decrease in egg-specific Th2-type Tfh and an expansion of Tregs with a gut-homing phenotype. The table below indicates the fluorescence-labeled monoclonal antibodies will be utilized for immunophenotyping the T cell population:

Live/Dead	Live CD4+ Lymphocytes
CD3	
CD4	
CD154	Antigen-specificity
CD25	Tregs
CD127	
IL-10	
IL-4	Th2
IL-13	
IFN-γ	Th1
CXCR5	Tfh
CCR6	Mucosal homing
CCR4	Skin homing

Staining Panel for T cell Phenotyping

CD154+ cells will be quantified per million CD4+ T cells. The profile of these cells will be quantified in two ways: the number of CD154+ cells of each phenotype (for example IL-4+ or IL-13+, or CD25^{High} CD127^{low}) per million CD4+ T cells, and the proportion of CD154+ cells of each phenotype. CD154+ cells induced by egg will be compared to those induced by CD3/CD28 stimulator beads. In addition, CD154+ cells induced by egg before and after immunotherapy will be compared.

8.2 Basophil Studies

Allergen desensitization has been shown to induce basophil hyporesponsiveness to allergeninduced degranulation, however, chronic exposure to allergens is also associated with constitutively activated basophils. We will use flow cytometry-based assessment of basophil activation/ degranulation longitudinally with and without in vitro stimulation to track changes induced by OIT and their relationship to clinical desensitization and sustained unresponsiveness.

At each time point, 0.5 ml of whole blood will be stimulated as follows:

- Medium alone
- Medium w/ 2 ng/ml human IL-3 (basophil medium)
- Basophil medium w/ 1 µM fMLP
- Basophil medium w/ $0.001 \ \mu g EW$
- Basophil medium w/ $0.01 \ \mu g EW$
- Basophil medium w/ $0.1 \ \mu g \ EW$
- Basophil medium w/ 1 µg EW
- Basophil medium w/ 1 µg anti-IgE

After a 30 minute incubation, cells will be stained, fixed, and shipped on ice to the central lab. Samples will be analyzed by flow cytometry for surface expression of activation markers (CD63, CD203c, and CD69). Basophils will be identified as CD203+ CD123+ lineage marker (CD3, CD19, CD14, and CD41) negative.

8.3 Egg-specific antibody

Antigen immunotherapy has been shown to induce antigen-specific humoral responses. The balance of isotypic response may play a role in allergen sensitivity (e.g., an increase of IgG/IgE).

At each of the mechanistic time points, a sample of plasma will be stored for assessment of eggspecific antibody levels.

We will measure total IgE and specific IgE and IgG4 by UniCAP from each time point. Egg specific IgE and IgG4 blood draws will be measured at the screening (Visit 00), 3 month (Visit 02), 6 month (Visit 03), the 1 year visit (Visit 04) and 16 months (Visit 05), 20 months (Visit 06), at the 2 year visit (Visit 07) and at the 2 year sustained unresponsiveness visit (Visit 08), if applicable.

8.4 Microarray

Changes in antibody repertoire within isotype subsets may also correlate with clinical outcome. Epitope repertoire can be partially characterized using peptide array-based immunoassay. For microarray analysis, overlapping peptides 20 amino acids in length with an offset of 2 residues and covering the full sequence of the major egg allergens (ovomucoid and ovalbumin; approximately 260 peptides in total) will be robotically arrayed in triplicate to reactive substrates (chemically modified glass slides). Purified whole allergen will be printed to serve as positive controls. These arrays will be used to probe for epitope-specific IgE and IgG from subject plasma (<20 μ L) at each time point. Bound IgE and IgG antibodies will be detected using fluorochrome-tagged secondary monoclonal antibody. Fluorescence emission will be measured using a GMS 418 Array Scanner (Affymetrix) and analyzed using commercial and custom software. The average plus 2 SD log intensity of the negative control elements will be used as an intra-slide cutoff to establish background. Array elements with CV >30% will be excluded from analysis. An inter-slide cutoff will be calculated as the average plus 2 standard deviation intensity of the corresponding signal from non-atopic control sera.

The primary endpoint will be the number of distinct IgG4- and IgE-binding epitopes to egg proteins at each time point. The number of epitopes will be compared longitudinally to baseline during immunotherapy between subjects receiving active treatment vs. placebo as well as between those who become tolerant vs. those who do not.

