Peanut OIT studies conducted at Duke University and Arkansas Children's Hospital support the concept that sustained unresponsiveness can be achieved by a long period of OIT. In these studies, 9 of the original 29 subjects reached the 2.5 year point in the study. The study was designed where subjects who were on OIT longer than 2.5 years and who had a peanut IgE less than 2 kU_A/L, would have a food challenge while on therapy, then if they passed the challenge, they were taken off the OIT. One month later, they would have a food challenge off-therapy. If they passed this challenge, they would introduce peanuts into their diet. For the 9 subjects, 6 of them had a peanut IgE < 2 kU_A/L and followed the above protocol. All 6 have passed both challenges and have peanuts in their diet. Beyond the 2 year time frame, the peanut IgE continues to decline in all subjects (personal communication Drs. [name] and [name]).³⁷ Two-thirds of subjects developed sustained unresponsiveness after 2.5 years on therapy. Additional studies with larger cohorts and longer follow-up will be required to characterize the development of sustained unresponsiveness or tolerance with active OIT over time.

The current protocol is based on the concept that Baked Egg and Egg OIT for children who have food allergy is a practical and safe method of active treatment. The study is designed to compare 2 different treatment forms of immunotherapy that have already been shown to induce sustained unresponsiveness in egg allergic children. This is a comparative protocol to assess best practice, not determine whether one or the other is better than placebo, which has already been established.

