For each of the planned assay points, we will compare treatment differences in the Egg OIT vs. Baked Egg treated subjects, and in those who achieve sustained unresponsiveness vs. those who fail to develop sustained unresponsiveness. We will assess each with univariate nonparametric statistics and where applicable repeated measure methods will be applied with suitable transformations as necessary.

Those assay endpoints with detected treatment differences will be considered Baked Egg or Egg-OIT affected endpoints. Subsequently, we will evaluate whether immune states, as measured by the mechanistic assays, are predictive of the tolerized and/or desensitized states.

Our hypotheses are based on the probability that Baked Egg therapy and Egg OIT will induce immunologic changes in egg-allergic subjects that will result initially in *desensitization* and eventually with prolonged administration, the development of sustained unresponsiveness to egg.

Hypothesis 1: The development of clinical sustained unresponsiveness to egg is associated with a reduction in allergen-specific Th2 effector cells, an increase in allergen-specific T regulatory (Treg) cells, and an induction of allergen-specific T follicular helper (Tfh) cells.

Antigen-specific CD4+ T cells can be identified by their upregulation of CD154 in response to short-term antigen re-stimulation *in vitro*. We expect that egg immunotherapy leading to sustained unresponsiveness will be associated with sustained changes in the adaptive immune response to egg. We anticipate that Th2 cells that provide T cell help to B cells in support of IgE class-switching will be lost, leading to the eventual decline in allergen-specific IgE. We anticipate that egg-specific Tregs will be induced, contributing to the suppression of the Th2 response. This is based on literature showing that children who have outgrown their milk allergy have increased CD4⁺ CD25⁺ cells after milk challenge, and that depletion of these cells enhances proliferation of milk-specific effector cells. In addition, we expect that boosting of IgG4 levels in response to immunotherapy will be associated with the expansion of egg-specific CD4⁺ T cells bearing markers of T follicular helper cells. We anticipate that these 3 changes participate in development of sustained unresponsiveness and will therefore correlate with clinical outcome.

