- 2. We will determine food-specific IgE and IgG4 to egg as the allergy persists or resolves. Additionally, we will follow titrated prick skin testing to egg.

The primary analysis of these studies will be the number of distinct IgG4- and IgE-binding epitopes to egg proteins defined by microarray immunoassay at each time point. These will be compared longitudinally to baseline in a repeated measures poisson regression model using a generalized linear model with poisson link function.

Secondary analysis will evaluate:

- 1. The change in egg-specific immunoglobulin isotypes.
- 2. Correlation between successful induction of sustained unresponsiveness (primary clinical endpoint) and baseline and final IgE and IgG4 epitope diversity.
- Correlation between specific epitope recognition patterns (baseline and final as defined by hierarchical clustering of microarray data⁸⁶) and induction of sustained unresponsiveness.
- 4. Correlation between successful induction of sustained unresponsiveness vs. baseline and final specific immunoglobulin isotypes.

We expect that subjects developing sustained unresponsiveness will develop an increase in the number of epitopes bound by IgG4 antibodies compared to epitopes bound by IgE antibodies, and that this will be accompanied by a rise in total egg-specific IgG4/IgE ratio.

Hypothesis 4: Sustained unresponsiveness will be associated with a predictive transcriptional signature detectable in whole blood or allergen restimulated PBMCs. Transcriptional profiling approaches allow for an unbiased analysis of gene expression, and through pathway analysis provides an opportunity to uncover novel and unexpected mechanisms that may contribute to immune tolerance. It is a complementary approach to the hypothesis-based studies outlined previously, and one that we will pilot herein. We anticipate that whole blood transcriptional profiling will reflect antigen-induced reprogramming of the immune response driven by *in vivo* delivery of antigen during OIT. In order to test that hypothesis, we will isolate RNA from whole blood obtained at baseline and time-points throughout immunotherapy. Our first objective is to determine if we can obtain a transcriptional signature of egg allergy by microarray analysis. We will perform a pilot experiment running samples from 3 groups of subjects: Egg-tolerant subjects (obtained through CoFAR8), baked egg reactive, and baked egg tolerant. The latter two groups

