9.3 Sample Size and Power Calculations

The sample size target for the randomized portion of the study is 96 individuals with 1:1 random assignment to Baked Egg and Egg OIT. The sample size was selected to determine whether a

difference exists between the treatment groups in the primary endpoint rate for the sustained unresponsiveness-focused portion of the study. Specifically, the sample was designed to have 85% power to detect with a two-sided 5% level test, a difference between a 40% and 70% sustained unresponsiveness rate. While a small dropout rate may occur, we will use all randomized cases who initiate treatment in the intent-to-treat analysis of the primary endpoint; failures associated with noncompliance are include in the denominator for event rates above.

This sample size is sufficient to address the secondary endpoint of the desensitization components of the study for event rate differences of comparable size.

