2.1 Purpose of the Analyses

The purpose of this trial is to assess the efficacy and safety of eOIT compared to baked egg in egg allergic but baked egg tolerant participants. This is an unblinded multicenter randomized trial without a placebo control. Baked egg tolerant participants were randomized to receive either eOIT or baked egg daily. An OFC will be performed at Year 2 to assess desensitization followed by an OFC off-therapy with an open feeding to assess sustained unresponsiveness (the primary efficacy endpoint). In addition, 40 baked egg intolerant participants were enrolled and assigned to eOIT to facilitate comparison of the efficacy and safety of eOIT in baked egg tolerant compared to baked egg intolerant participants. Secondary endpoints address safety and alternate measures of efficacy as well as immunologic comparisons. The timing of the analyses are defined in Section 6.2.

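### The epitope analysis names a placebo contrast the trial cannot make, and leaves the epitope counting rule and the Poisson variance unstated

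*Protocol*

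**What the plan says.** Protocol Section 8.4 takes as its endpoint the number of distinct epitopes bound by IgG4 and by IgE. It says the counts will be "compared longitudinally to baseline during immunotherapy between subjects receiving active treatment vs. placebo", and adds a second comparison of subjects who become tolerant with those who do not. The array uses "overlapping peptides 20 amino acids in length with an offset of 2 residues", about 260 peptides in all. Section 8.4 names no statistical model.

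The model is in Protocol Section 2.1, under Hypothesis 3: "These will be compared longitudinally to baseline in a repeated measures poisson regression model using a generalized linear model with poisson link function". That sentence describes change from baseline and has no treatment term. Earlier in Section 2.1, the introduction to the mechanistic objectives says that for every assay "we will compare treatment differences in the Egg OIT vs. Baked Egg treated subjects", and likewise subjects with and without sustained unresponsiveness (SU). Nonparametric tests are planned there, with repeated-measures methods where applicable.

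On the design, Protocol Section 9.3 says: "The sample size target for the randomized portion of the study is 96 individuals with 1:1 random assignment to Baked Egg and Egg OIT". SAP Section 2.1 says: "This is an unblinded multicenter randomized trial without a placebo control". Protocol Section 1.2 says: "This is a comparative protocol to assess best practice, not determine whether one or the other is better than placebo".

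The SAP keeps the epitope hypothesis among its tertiary objectives (Section 3.1). However, its derived variables (Section 3.3) include no epitope count, and Section 11 covers only skin prick tests, immunoglobulins, basophils and flow cytometry. Protocol Section 9.5 calls the mechanistic work exploratory, sends the reader back to Section 2 for the analysis strategies, and sets a 0.01 significance level.

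**The concern.** An analyst looking for the epitope plan finds three descriptions that do not agree: a placebo comparison (Section 8.4), a between-arm comparison (Section 2.1, introduction to the mechanistic objectives) and a change from baseline (Section 2.1, Hypothesis 3). The one in the assay's own section cannot be carried out.

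The model text is also incomplete. Poisson is a distribution, not a link; the usual link is log. No correlation structure, robust variance or overdispersion term is given. This matters because one antibody specificity can light up a run of overlapping peptides. Whether that run counts as one epitope or as several changes the variance of the outcome, and so the error rate of any test that takes the Poisson variance at face value. Section 9.5 relies on the 0.01 level to limit false positives, and that protection depends on the standard errors being right.

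**Working it through.** **1. The contrast.** The randomized arms are Baked Egg and Egg OIT, 96/2 = 48 each, plus a non-randomized Egg OIT group (Protocol Sections 9.3 and 9.4). Placebo is used only inside the blinded food challenges (Protocol Sections 6.5 to 6.7). No subject receives placebo as treatment, so the first contrast in Section 8.4 has no comparator.

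**2. Overlap.** Neighbouring peptides share 20 − 2 = 18 of 20 residues. The documents give no epitope length, so 6 to 15 residues is assumed. The table's second column is the number of 20-residue peptides, placed every 2 residues, that wholly contain an epitope of that length.

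**3. Dispersion.** The documents give no variance figure for this analysis, so there is none to reproduce. Arrays of 260 peptides were simulated, 4,000 per setting. Epitopes were placed at random, their number was Poisson with mean 5 or 10, and every subject had the same mean. The ratio φ is variance divided by mean; a Poisson count has φ = 1.

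| Epitope length | Peptides containing it | φ, positive peptides (mean 5; 10) | φ, adjacent positives merged (mean 5; 10) |
|---|---|---|---|
| 6 | 7–8 | 6.65; 5.23 | 0.76; 0.56 |
| 8 | 6–7 | 5.50; 4.79 | 0.75; 0.58 |
| 10 | 5–6 | 4.75; 4.45 | 0.77; 0.65 |
| 12 | 4–5 | 4.14; 3.75 | 0.84; 0.70 |
| 15 | 3 | 2.85; 2.65 | 0.89; 0.78 |

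**4. Effect on the test.** With model-based Poisson variance, the true standard error is √φ times the reported one. The true level of a two-sided nominal 0.01 test is 2 × [1 − Φ(2.576/√φ)].

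- Positive peptides, φ = 2.65: √φ = 1.63, true level about 0.11.
- Positive peptides, φ = 6.65: √φ = 2.58, true level about 0.32.
- Merged, φ = 0.89: 2.576/0.943 = 2.73, true level about 0.006.
- Merged, φ = 0.56: 2.576/0.748 = 3.44, true level about 0.0006.

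Overlap therefore inflates the error rate under one counting rule and lowers it under the other.

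**5. Differences between subjects.** With an assumed between-subject coefficient of variation of 0.5, φ is 6.0 to 15.6 for peptides and 1.3 to 2.2 after merging. The excess over 1 in the merged counts comes from subject differences, not from overlap.

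**6. Whole-trial check.** 400 null trials were simulated with 48 per arm, two visits, 10-residue epitopes, a mean of 8 epitopes and the same coefficient of variation of 0.5. Rejection rates for treatment-by-visit at nominal 0.05 / 0.01 were:

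| Count | Poisson, model-based variance | Poisson GEE, robust standard errors |
|---|---|---|
| Positive peptides | 0.345 / 0.220 | 0.062 / 0.010 |
| Adjacent positives merged | 0.015 / 0.000 | 0.065 / 0.013 |

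Monte Carlo error near 5% is √(0.05 × 0.95/400), about 1 percentage point. The 0.345 / 0.220 agrees with the formula in step 4, which gives 0.327 / 0.198 at φ = 4 and 0.381 / 0.249 at φ = 5.

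**The case against.** The strongest reply is that little is broken. Section 2.1 already sets Egg OIT versus Baked Egg and SU versus no SU for every assay, and the Section 8.4 sentence itself goes on to a feasible comparison by tolerance status. A reader might infer that the between-treatment question on epitopes has no usable contrast at all. The documents do not support that. What stands is that the assay-specific section states an impossible contrast and conflicts with the general one.

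A reader might also infer that peptide overlap is bound to make the error bars too narrow. That does not follow. The stated endpoint is distinct epitopes, not positive peptides, and merging reverses the overlap effect. Nor is the plan a plain Poisson regression: it specifies repeated measures, and a GEE with robust standard errors is a standard way to fit that and stays close to nominal. Section 8.4 names no model, and the between-group tests in Section 2.1 are partly nonparametric. What stands is that neither the counting rule nor the variance estimator is written down. Repeated measures could equally mean a subject random intercept, which would not absorb clumping within a visit (this is reasoned, not simulated).

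Finally, SAP Section 12 allows some mechanistic endpoints to be described further as data become available. The gap can therefore still be closed, but the current text does not close it.

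**Conclusion.** The concern holds as a minor inconsistency and specification gap. The placebo contrast in Section 8.4 is impossible with these arms; that rests on the documents alone and needs no assumption. The Poisson plan misnames its link, gives no variance estimator and has no rule for turning neighbouring positives into one epitope, and the SAP supplies none of these.

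The size of the second part is conditional. If positive peptides are counted with model-based variance, the true level at nominal 0.01 is about 0.11 to 0.32. If adjacent positives are merged, overlap alone leaves the test slightly conservative. These figures rest on assumed epitope lengths of 6 to 15 residues, randomly placed epitopes averaging 5 or 10 per subject, and a two-sided test. The whole-trial check also assumes the between-subject variation. The analysis is tertiary and exploratory, so the primary endpoint and its power are untouched.

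**What to change.** 1. In Protocol Section 8.4, replace the placebo contrast with eOIT-Randomized versus Baked Egg, and compare SU with non-SU adjusted for treatment.
2. Define the count: a run of adjacent positive peptides is one epitope. Note the price, which is that nearby epitopes can be joined. In the simulation, 5 true epitopes gave merged means of 4.3 to 4.6, and 10 gave 7.5 to 8.7.
3. Replace the model sentence in Section 2.1 with a log-link Poisson GEE with robust standard errors, or a negative binomial model, for post-baseline counts adjusted for the baseline count, treatment (or SU status) and visit. This matches the form SAP Section 11 already uses for the other blood assays.
4. Add the count to SAP Section 3.3 and the analysis to SAP Section 11, at the 0.01 level.

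The cost is a few lines in each document and standard software. No new data or samples are needed.
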